12.4.2. Analysis Addressing the Primary Efficacy Endpoint

The primary analysis will be conducted via a fully covaried logistic regression analysis of the PSNHDD during Study Weeks 22 to 25 (last 4 weeks of the maintenance period on the mITT population). The model includes treatment group, clinical site, pre-randomization drinking goal (abstinence versus not abstinent), and baseline percent heavy drinking days (in the 28-day period prior to the date that the subject signed the informed consent form). Exploratory analyses will examine other timeframes beyond the last 4 weeks. A two-tailed p-value < 0.05 will be considered statistically significant. The primary analysis will use all mITT subjects and will employ imputation for missing drinking data such that any subject with any missing drinking data during the evaluation period for this endpoint will be imputed as a subject with a heavy drinking day.

Prior to the subject dropping out of the study, every attempt will be made to continue to collect TLFB data; however, if the subject does not want to participate in the collection of the TLFB they will be asked to participate in a periodic follow-up phone call to collect a summary of drinking information. If the subject agrees to be contacted then they will be asked about any drinking and heavy drinking during the time since last contact. Phone calls will continue until the end of the treatment period, as deemed acceptable by the patient. The two questions cover whether the subject had any heavy drinking days or drinking days during the period covered. This summary drinking data will be used for the primary endpoint when TLFB data are not available. If the subject does not agree to participate with phone contact, thus no summary drinking data nor TLFB data is available, then imputation as indicated above will be used. An

analysis of PSNHDD without imputation for missing data will be performed as an exploratory analysis.

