Primary: The primary outcome measure examines the hypothesis that HORIZANT Extended-Release Tablets will increase the PSNHDD compared to placebo during the last 4 weeks of the maintenance period (Study Weeks 22-25). A "heavy drinking day" is 4 or more drinks per drinking day for women and 5 or more drinks per drinking day for men. Drinking data will be collected by the Timeline Followback (TLFB) method. If during the last 4 weeks of the maintenance period of the study, the subject does not come back for clinic visits or provide TLFB data but agrees to telephone contact, then the subject will be asked if there were any heavy drinking days during the final study period. These data will be used to determine the primary efficacy endpoint when TLFB data are missing, otherwise the data will be imputed as having a heavy drinking day during this period.

Secondary: Secondary efficacy endpoints will also be analyzed over the last 4 weeks of treatment.

- 1. Percentage of subjects abstinent from alcohol (key secondary endpoint)
- 2. Percentage of subjects with a World Health Organization (WHO) drinking risk category decrease of:
 - a. at least 1-level
 - b. at least 2-levels
- 3. Percentage of days abstinent per week
- 4. Percentage of heavy drinking days per week
- 5. Weekly mean number of drinks per week
- 6. Weekly mean drinks per drinking day
- 7. Cigarettes smoked per week among smokers
- 8. Alcohol craving score [Alcohol Craving Scale Short Form (ACO-SR-R)]
- 9. Alcohol related consequences (ImBIBe) score
- 10. Pittsburg Sleep Quality Index (PSQI) score
- 11. Beck Anxiety Inventory (BAI) score
- 12. Beck Depression Inventory Scale II (BDI-II) score

Safety Endpoints Safety endpoints will be evaluated over the entire treatment and follow-up periods.

- 1. Vital signs
- 2. Blood chemistries
- 3. Urine drug screen results
- 4. Blood alcohol concentration (BAC) by breathalyzer
- 5. AEs
- 6. Electrocardiogram (ECG) results

- 7. Clinical Institute of Withdrawal Alcohol Revised (CIWA-AR) scores
- 8. Profile of Moods States (POMS) scores
- 9. Frequency of subjects with suicidal ideation at any time during the treatment period –Columbia-Suicide Severity Rating Scale (C-SSRS)

Compliance: Self report of compliance with investigational products and gabapentin plasma levels.

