11.11. Drinking Question

If a subject is withdrawn from the study early and is no longer participating in clinic visits or providing TLFB drinking data but is willing to be contacted by phone at the week most proximal to dropout, then they will be asked about any drinking and heavy drinking during the time since last contact. Phone calls will continue until the end of the treatment period, as deemed acceptable by the patient, to obtain data on the primary efficacy endpoint (any heavy drinking days defined as 5 drinks per day for males and 4 drinks per day for females) and on the secondary efficacy

endpoint of abstinence. The rules regarding standard drinking units (SDU) applies. This data will be recorded on a source document and eCRF. This does not apply to subjects who are willing to supply daily drinking data by the TLFB method.

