12.4.3. Secondary Efficacy Endpoints Analysis

12.4.3.1. Key Secondary Endpoint: Percentage of Subjects Abstinent from Alcohol

Percentage of subjects abstinent during Weeks 22 to 25 is the key secondary endpoint. Covariates for percentage of subjects abstinent will be the same as those for the primary endpoint PSNHDD as described in Section 9.4.2. Fewer covariates for the logistic regression may be used depending upon the number of events. If the number of events permits the inclusion of a baseline drinking covariate, the percentage of days abstinent will be used as the covariate for the percent subjects abstinent endpoint. The testing procedure utilizes the serial gate keeping methodology (Dmitrienko and Tamhane-2009). The key secondary endpoint can only be evaluated for statistical significance after the primary endpoint has been identified as statistically significant. In this situation, percentage of subjects abstinent will be evaluated using the Wald statistic from the logistic regression model at p<0.05 after PSNHDD is found to have p<0.05. If PSNHDD is not statistically significant at the 0.05 level then no significance testing of percentage of subjects abstinent will be performed. This analysis will be performed on mITT subjects with no imputation for missing data. However, if drinking data are missing by TLFB, but the subject reports any drinking during Weeks 22 to 25 using the Drinking Question eCRF, then the subject will be considered not abstinent. An analysis of percent subjects abstinent without imputation for missing data will be performed as an exploratory analysis.

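### The Drinking Question is asked over the time since the previous contact but scored on Weeks 22-25, so a yes that spans either end of that window can miscode a responder

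*Protocol*

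**What the plan says.** The primary endpoint is the percentage of subjects with no heavy drinking day in Study Weeks 22-25. When TLFB is unavailable, Section 12.4.2 substitutes the Drinking Question: "This summary drinking data will be used for the primary endpoint when TLFB data are not available".

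Two places define the question by contact interval:
- Section 12.4.2: "If the subject agrees to be contacted then they will be asked about any drinking and heavy drinking during the time since last contact".
- Section 11.11: "then they will be asked about any drinking and heavy drinking during the time since last contact". The same section says the calls continue "as deemed acceptable by the patient, to obtain data on the primary efficacy endpoint", and then adds abstinence.

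Two places treat the answer as relating to the endpoint window:
- Synopsis, Criteria for Evaluation (Primary): "the subject will be asked if there were any heavy drinking days during the final study period". The sentence opens with a condition about the last 4 weeks of maintenance, so the final period is naturally read as Weeks 22-25.
- Section 12.4.3.1, on the key secondary endpoint, relies on whether "the subject reports any drinking during Weeks 22 to 25 using the Drinking Question eCRF".

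On the form of the answer, Section 12.4.2 says: "The two questions cover whether the subject had any heavy drinking days or drinking days during the period covered". On timing it says: "Phone calls will continue until the end of the treatment period, as deemed acceptable by the patient". Table 5 places the question at the clinic-visit columns, including Weeks 20, 24, 26 and 27, and a footnote limits it to subjects who no longer attend visits and will not give TLFB.

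**The concern.** The collection interval and the scoring window are different things, and the protocol does not join them. No section requires a contact at the start of Week 22, tells the caller to limit recall to Weeks 22-25, or says how to code a yes that also covers other days.

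The error runs one way. A no over a longer interval is still true of every window day inside it. A yes may rest only on days outside the window and still be scored as a heavy drinking day inside it. As the protocol describes it, the answer is a summary for the whole interval. Knowing the start and end dates of the interval would not show on which side of the boundary the heavy day fell, so an analysis rule written later could not repair the record.

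At stake is the correct coding of individual subjects on the primary endpoint. The any-drinking item raises the same problem for the key secondary endpoint, abstinence in Weeks 22-25.

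**Working it through.** **Calendar.** Week n Day 1 is study day 7(n − 1) + 1. This gives Week 20 = Day 134, Week 22 = Day 148, Week 24 = Day 162, Week 26 = Day 176 and Week 27 = Day 183. The window is Days 148-175. Section 8.7 prefers visits on the weekday of the first dose, so nominal contacts fall on Day 1 of a week. Recall is taken to run from the previous contact to the day before the current one, as Section 11.33 specifies for TLFB; for the Drinking Question this is an assumption.

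**Start of the window.**
- Contact on Week 22 Day 1: 0 days of the next interval precede the window.
- Only contacts at Weeks 20 and 24: recall is Days 134-161, 28 days, of which Days 134-147 (14) precede the window. If the Week 20 contact is k = 0 to 3 days later in its week (the visit window in Section 8.7), 14 − k = 11 to 14 days precede it.
- Weekly calls: zero if one falls on Week 22 Day 1. Otherwise at most 6 days, since a 7-day interval that straddles the boundary must contain at least one window day.

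**End of the window.** If the previous contact was Week 24 Day 1, a Week 27 Day 1 contact covers Days 162-182, 21 days. Of these, Days 176-182 (7 taper days) fall after Week 25. If there was a contact on Week 26 Day 1, that contact's recall ends on Day 175 and does not overrun, and the Week 27 interval (Days 176-182) lies wholly outside the window.

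**Planned power, reproduced.** Section 12.5 gives 13% and 27%, 173 per arm, two-sided 0.05 and 91% power. With pooled variance under the null and no continuity correction:

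z = [0.14 × √173 − 1.96 × √(2 × 0.20 × 0.80)] / √(0.13 × 0.87 + 0.27 × 0.73) = (1.841 − 1.109) / 0.557 = 1.316, so power = 90.6%.

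This agrees with the stated 91%.

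**Subjects affected.** False failures per arm = 173 × 0.15 × s × q × f × rate × r.
- 15% dropout is from Section 12.5; 173 × 0.15 = 25.95 subjects per arm.
- rate is the completer response implied by counting all dropouts as failures: 0.13/0.85 = 15.3% on placebo and 0.27/0.85 = 31.8% on drug.
- s, the share of dropouts with a straddling interval: 0.5-1 (assumed).
- q, the share who refuse TLFB but answer the question: 0.1-0.5 (assumed).
- f, their in-window response relative to completers: 0.5-1 (assumed).
- r, the share of window-clean subjects with a heavy day elsewhere in the interval: 0.1-0.5 (assumed).

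| | Placebo | Drug |
|---|---|---|
| All inputs low | 25.95 × 0.0025 × 0.153 = 0.01 | 25.95 × 0.0025 × 0.318 = 0.02 |
| All inputs high | 25.95 × 0.25 × 0.153 = 0.99 | 25.95 × 0.25 × 0.318 = 2.06 |

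**Power under these inputs.** If every such subject is failed, the rates are the planned 13%/27% and power is 90.6%. With s = 1, q = 0.5, f = 1 and no false failure (r = 0), the rates are 14.15%/29.38% and power is 93.3%. With r = 0.5 they are 13.57%/28.19% and power is 92.0%.

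**The case against.** Collecting since the previous contact and scoring by window need not conflict. The calls can begin long before Week 22, and exploratory analyses use other periods. The synopsis already describes a question aimed at the final period, so miscoding arises only where a site follows 11.11 and 12.4.2 instead. That is fair, but 11.11 and 12.4.2 are the operative text for the caller and for the primary analysis, and neither sets the limit.

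The 14-of-28 figure needs the weekly calls to have stopped or not to count. Section 6 plans weekly telephone contact and Table 5 shows calls in Weeks 21-23; if these continue and reset the recall, the overlap is a few days or none. This stands, and the figure is therefore conditional. The telephone script in Section 8.10 does not contain the Drinking Question, and the protocol does not say whether such a call counts as the previous contact.

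The eCRF is not shown and may record more than the protocol describes. That also stands. Interval dates alone would not settle a straddling yes, but a dated answer would.

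Finally, a false yes receives the same code as missing data, and the 13%/27% already count all dropouts as failures. This is correct for the imputed primary analysis and is why power is safe. It does not hold where nothing is imputed: the exploratory analysis in Section 12.4.2, and the key secondary analysis as Section 12.4.3.1 describes it (the synopsis counts missing data as non-abstinent). There a false yes turns a subject who would have been left unimputed into a failure.

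**Conclusion.** The point holds as a mismatch between the interval over which the question is asked (11.11, 12.4.2) and the window on which it is scored (synopsis, 12.4.3.1). A yes that spans either end of Weeks 22-25 can code a true responder or abstainer as a failure. The number affected is small, roughly 0 to 2 per arm, and that range rests on four assumed inputs.

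Three stronger readings are not supported:
- A reader might infer three competing recall periods. Read in context, the synopsis and 12.4.3.1 name the same window, so there are two.
- A reader might infer that half the recall lies outside the window on the planned schedule. That requires contacts only at Weeks 20 and 24.
- A reader might infer lost power or a biased comparison. Power stays at or above plan (90.6% to 93.3% in the cases computed), and nothing in the protocol shows that miscoding would differ between arms.

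The change is worth making because the answer enters the primary and key secondary endpoints and, as described, could not be corrected after collection.

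**What to change.** In Sections 11.11 and 12.4.2 and in the Drinking Question eCRF, state that for any contact whose recall interval crosses the start of Week 22 or the end of Week 25, the heavy-drinking and any-drinking questions are asked separately for days inside and days outside Weeks 22-25. Score the primary and key secondary endpoints only on the in-window answers. Both ends need bounding, because Table 5 also places the question at Week 27, after taper. Align the synopsis and Section 12.4.3.1 with this wording.

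The cost is one extra date prompt in the call script and eCRF, plus aligned text in four places. Visits, sample size and the analysis model do not change.

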12.4.3. Secondary Efficacy Endpoints Analysis

12.4.3.1. Key Secondary Endpoint: Percentage of Subjects Abstinent from Alcohol

Percentage of subjects abstinent during Weeks 22 to 25 is the key secondary endpoint. Covariates for percentage of subjects abstinent will be the same as those for the primary endpoint PSNHDD as described in Section 9.4.2. Fewer covariates for the logistic regression may be used depending upon the number of events. If the number of events permits the inclusion of a baseline drinking covariate, the percentage of days abstinent will be used as the covariate for the percent subjects abstinent endpoint. The testing procedure utilizes the serial gate keeping methodology (Dmitrienko and Tamhane-2009). The key secondary endpoint can only be evaluated for statistical significance after the primary endpoint has been identified as statistically significant. In this situation, percentage of subjects abstinent will be evaluated using the Wald statistic from the logistic regression model at p<0.05 after PSNHDD is found to have p<0.05. If PSNHDD is not statistically significant at the 0.05 level then no significance testing of percentage of subjects abstinent will be performed. This analysis will be performed on mITT subjects with no imputation for missing data. However, if drinking data are missing by TLFB, but the subject reports any drinking during Weeks 22 to 25 using the Drinking Question eCRF, then the subject will be considered not abstinent. An analysis of percent subjects abstinent without imputation for missing data will be performed as an exploratory analysis.

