The key secondary endpoint is the percentage of subjects abstinent during Weeks 22 through 25 on the mITT population. The analysis will be performed using a fully covaried logistic regression that includes treatment group, clinical site, pre-randomization drinking goal (abstinence versus not abstinent), and baseline percent days abstinent as covariates; however, fewer covariates may be included given a limited number of observed events. Subjects with any missing drinking data during Weeks 22 to 25 will be considered non-abstinent. Statistical significance will be evaluated if and only if the primary endpoint (PSNHDD) is statistically significant (p<0.05). The testing procedure utilizes serial gate keeping methodology (Dmitrienko and Tamhane 2009). If statistical significance for the primary endpoint of PSNHDD is met then the Wald statistic from the fully covaried logistic regression will be used to test treatment differences in the percentage of subjects abstinent with statistical significance identified with a two-tailed p-value below 0.05.

Analysis of the Supportive Secondary Endpoints:

Secondary endpoints will compare the HORIZANT Extended-Release Tablets group with the placebo group using mixed-effects models. Covariates for continuous secondary efficacy endpoints include the baseline equivalent of the endpoint, clinical site, treatment, time and the treatment by time interaction. Additional covariates for the secondary efficacy endpoints may include baseline characteristics with a theoretical and/or empirical basis for a relationship with a particular secondary endpoint. In general, every continuous secondary efficacy endpoint is analyzed using a repeated measures mixed effects model where subjects are random effects; factors and covariates are fixed effects. The overall least squares means and least square means for each time point along with the 95% confidence intervals will be presented for the untransformed endpoint only, while two-tailed p-values and Cohen's d will be presented for both the untransformed and transformed data. Inference and Cohen's d will be based upon the results using

appropriately transformed data. Percent subjects with a WHO 1-level decrease in alcohol consumption and a WHO 2-level decrease in alcohol consumption will be analyzed via a fully covaried logistic regression of the endpoint measured during the last 4 weeks of the maintenance period. No imputation will be used for the analysis of secondary endpoints.

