12.4.11. Multiple Comparison/Multiplicity

The primary endpoint and key secondary endpoint use the serial gate keeping methodology (Dmitrienko and Tamhane 2009) to maintain a family-wise Type I error of 0.05. This process requires an ordering of the hypotheses; namely, that the primary hypothesis for PSNHDD is evaluated first, followed conditionally by the key secondary hypothesis for percentage of subjects abstinent. This procedure requires that the primary hypothesis be rejected at p<0.05 then the hypothesis for the key secondary endpoint may be evaluated. If the primary hypothesis is not rejected then there is no test for the key secondary hypothesis. The serial gate keeping methodology indicates that if the primary hypothesis is rejected then the entire alpha (0.05, two-

sided) is available for the key secondary hypothesis. As such, the key secondary endpoint of percentage of subjects abstinent is evaluated at p<0.05 (two-sided) for statistical significance.

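### The key secondary (abstinence) test has two incompatible missing-data rules: missing counts as non-abstinent in the synopsis, no imputation in section 12.4.3.1

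*Protocol*

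**What the plan says.** The synopsis, under the key secondary endpoint, describes a covaried logistic regression of abstinence in Weeks 22 to 25 on the mITT population, tested by the Wald statistic once the primary endpoint has succeeded. Its rule is: "Subjects with any missing drinking data during Weeks 22 to 25 will be considered non-abstinent".

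Section 12.4.3.1 describes the same endpoint, window, population, statistic and gate, and says: "This analysis will be performed on mITT subjects with no imputation for missing data". It adds one exception for subjects without TLFB data: "but the subject reports any drinking during Weeks 22 to 25 using the Drinking Question eCRF, then the subject will be considered not abstinent". The section then closes with: "An analysis of percent subjects abstinent without imputation for missing data will be performed as an exploratory analysis".

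Section 12.4.11 makes the test confirmatory at the full two-sided level: "As such, the key secondary endpoint of percentage of subjects abstinent is evaluated at p<0.05 (two-sided) for statistical significance". It does not mention missing data.

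For the primary endpoint, section 12.4.2 counts a subject with any missing drinking data as having a heavy drinking day, after using telephone answers where they exist: "This summary drinking data will be used for the primary endpoint when TLFB data are not available".

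**The concern.** Under the synopsis, a subject with missing data stays in the denominator as a failure. Under 12.4.3.1 the same subject leaves the analysis unless drinking was reported by telephone. These are different analyses with different denominators and different estimated rates.

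Section 12.4.3.1 also sits badly with itself. Once its main analysis is non-imputed, listing a non-imputed analysis as exploratory adds nothing. The parallel sentence for the primary endpoint in 12.4.2 ("analysis of PSNHDD without imputation for missing data will be performed as an exploratory analysis") makes sense because it follows an imputed main analysis.

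At stake is the prespecification of the only secondary test that carries alpha. With both rules in the protocol, either result could later be defended as the planned one.

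**Working it through.** **Can the texts be reconciled?**

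- *The Drinking Question exception in 12.4.3.1.* It reclassifies only subjects who report drinking. The synopsis fails everyone with any missing data. The conflict remains.
- *The synopsis sentence* "No imputation will be used for the analysis of secondary endpoints". It stands under the supportive secondary endpoints. Read more widely, it would make the synopsis contradict itself.
- *The sentence in 12.4.8 that abstinence is not imputed.* It follows the text on exploratory multiple imputation and does not say whether it reaches the gated test. Later in 12.4.8, primary and secondary endpoints over the whole maintenance period are to be analysed both with and without imputation, so it is hard to read as a blanket rule.

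None of these settles the matter.

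**The plan's own figure.** The protocol gives power only for the primary endpoint (12.5): 173 per group, 13% v 27%, two-sided 0.05, 91% power. With pooled variance under the null, power = Φ[(0.14√173 − 1.96√(2 × 0.20 × 0.80)) / √(0.13 × 0.87 + 0.27 × 0.73)] = Φ(1.316) = 90.6%. It reproduces and is not affected by this point. No figure is given for the key secondary endpoint, so what follows is illustration.

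**Inputs.** From 12.5: 173 per arm and 15% dropout in each arm. Assumed: abstinence of 20% (drug) and 10% (placebo) among subjects with data, held fixed; unadjusted analysis; gate ignored.

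**Equal missing data.**

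- Subjects affected: 0.15 × 346 = 51.9, about 52.
- No imputation: 20% v 10%, difference 10.0 points.
- Missing = non-abstinent: 0.20 × 0.85 = 17.0% and 0.10 × 0.85 = 8.5%, difference 8.5 points.

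**Worked Wald tests.** z = ln(OR) / √(1/a + 1/b + 1/c + 1/d), where a to d are the four cell counts. The abstainers stay the same; the denominators are subjects with data, or 173 per arm.

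For 28/138 v 16/156:

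- No imputation: OR = (28/110)/(16/140) = 2.23, SE = 0.338, z = 2.37, p = 0.018.
- Missing = non-abstinent: OR = (28/145)/(16/157) = 1.89, SE = 0.334, z = 1.91, p = 0.056.

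| Missing, drug / placebo | Abstinent among subjects with data, drug v placebo | p, no imputation | p, missing = non-abstinent |
|---|---|---|---|
| 15% / 15% | 29/147 v 15/147 | 0.024 | 0.026 |
| 16.5% / 13.5% | 29/144 v 15/150 | 0.017 | 0.026 |
| 11.5% / 18.5% | 31/153 v 14/141 | 0.016 | 0.008 |
| 10% / 20% | 31/156 v 14/138 | 0.023 | 0.008 |
| 20% / 10% | 28/138 v 16/156 | 0.018 | 0.056 |

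Only the last crosses 0.05.

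**Simulation.** 1,000,000 trials per setting, binomial missingness and abstinence, the same Wald test, success = two-sided p < 0.05 favouring drug. 0.5 was added to cells only when a success count was zero.

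| Missing, drug / placebo | Power, no imputation | Power, missing = non-abstinent | Verdicts differ |
|---|---|---|---|
| 15% / 15% | 67.0% | 65.6% | 5.0% |
| 16.5% / 13.5% | 67.2% | 61.0% | 7.2% |
| 13.5% / 16.5% | 66.8% | 70.1% | 5.3% |
| 18.5% / 11.5% | 67.4% | 54.5% | 13.0% |
| 11.5% / 18.5% | 66.6% | 75.6% | 9.3% |
| 20% / 10% | 67.3% | 49.4% | 17.9% |
| 10% / 20% | 66.5% | 79.3% | 12.8% |

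**Range over other rates.** Section 4.3.7 gives 12-week sustained abstinence of 17.0% (1800 mg), 11.1% (900 mg) and 4.1% (placebo) in an earlier gabapentin trial. Taken as rates among subjects with data, a rough guide only, verdicts differ as follows:

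- 17.0% v 4.1%: about 1% of trials at equal 15% missing, 1 to 4% at imbalances up to 10 points.
- 11.1% v 4.1%: about 4%, and 5 to 12%.

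**The case against.** The strongest reply concerns weight. Under the protocol's only dropout assumption the two tests almost agree, and at 17.0% v 4.1% they disagree in about 1% of trials. The 20% and 10% rates and every imbalance are assumptions. Sections 8.14.1.2, 11.11 and 11.33 continue drinking assessments after drug is stopped or the subject withdraws, which should limit missing data. The primary test is untouched, and the SAP that 12.1 requires before unblinding could choose a rule. All of this stands. It limits how often the verdict would change, but not the contradiction or the change in reported rates. A SAP author would also have to depart from one protocol text whichever rule was chosen.

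The figure of 52 equates dropout with missing data. Some dropouts will still give answers by telephone, and some who stay will have gaps. It is a rough proxy.

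It can also be said that the detailed statistical section should prevail over one synopsis sentence, so that correcting the synopsis would be an equally small edit. That is a legitimate choice, but it leaves the exploratory analysis in 12.4.3.1 without a purpose and separates the endpoint from the primary endpoint's rule.

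Finally, 12.4.3.1 does not say how a telephone report of no drinking is used. Section 11.11 says the calls also serve the abstinence endpoint, which suggests that answers count in both directions. This needs clarification and is not a further contradiction.

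**Conclusion.** The concern holds. The protocol prescribes two opposite missing-data rules for its only alpha-controlled secondary test, and nothing in it resolves them. At 15% missing in each arm the effect on the test is small (verdicts differ in about 5% of trials at assumed rates of 20% v 10%), but the reported difference moves from 10.0 to 8.5 points. Larger effects, up to 18% disagreement, require a 10-point imbalance that the protocol does not predict. These figures are unadjusted, ignore the gate and hold abstinence among subjects with data fixed. The conflict bears on inference only if the primary endpoint succeeds. It should be corrected because the test is confirmatory and must have one prespecified analysis.

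**What to change.** State one rule before unblinding, in the same terms in the synopsis and 12.4.3.1. The simplest course is to align 12.4.3.1 with the synopsis and the primary endpoint:

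- analyse all mITT subjects;
- use TLFB data first;
- where TLFB is missing, use Drinking Question answers covering Weeks 22 to 25, whether they report drinking or none;
- count anyone still missing as non-abstinent;
- keep the no-imputation analysis as the exploratory analysis already listed.

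In 12.4.8, add a phrase limiting the abstinence sentence to the exploratory multiple imputation.

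If the sponsor prefers no imputation, the synopsis sentence must be changed and the redundant exploratory sentence in 12.4.3.1 removed. Either way the cost is a wording change, with no new data.
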